hypothesize that tolerance induction with Eloctate ITI plus Emicizumab is superior to Eloctate ITI alone in eradicating inhibitors in children and adults with severe hemophilia A and inhibitors. **Objective:** The **Primary Objective** is to determine if Eloctate ITI plus Emicizumab is different from Eloctate ITI alone in eradicating inhibitors in severe hemophilia A patients with high-responding inhibitors who are ITI-refractory or ITI-naïve, or those arising during the Inhibitor Prevention Trial. The Secondary Objectives are to evaluate the safety and mechanism of Eloctate ITI plus Emicizumab vs. Eloctate ITI alone in eradicating inhibitor eradication. The Primary Endpoint is the probability of becoming inhibitor-free by 48 weeks, where the **Endpoints:** eradication of inhibitor formation is defined as anti-FVIII < 0.6 B.U. by chromogenic Nijmegen Bethesda assay (CBA). The Secondary Endpoints include a) safety by number and frequency of bleeding episodes (i.e. hematoma, joint, CNS bleed) and frequency and time to port infections; and b) mechanism of inhibitor suppression (eradication) by FVIII-specific T cell ELISPOT assay, B cell, Ig, and RNA assays and cytokine assays to determine the role of T regs in controlling immune response to FVIII; and by FVIII genotype; HLA type; and chromogenic FVIII trough levels; and by micriobiome stool sample, each compared with anti-FVIII. **Study Population:** Study subjects will be male adults and children age > 4 months of age with severe hemophilia A, defined as factor VIII < 0.01 IU/ml and a current or past high-responding inhibitor (anti-FVIII >5.0 B.U.), either ITI-refractory, ITI-naïve, or developing on the linked Inhibitor Prevention Trial. A total of 90 eligible severe hemophilia A patients with inhibitors will be enrolled in this 6-year trial. Site Enrolling Subjects: There are up to 41 participating sites: Hemophilia Treatment Center (HTCs). **Description of Study** There are two study interventions: Eloctate ITI plus Emicizumab vs. Eloctate ITI alone. Intervention: Recombinant factor VIII Fc (Eloctate[®]) is an FDA-approved clotting factor approved for treatment and/or prevention of bleeds in hemophilia A. It is an intravenous agent supplied as single-use vials containing approximately 250, 500, 750 IU per vial. The vials are reconstituted with 5-10 ml vial of sterile water for injection, USP, which is transferred by two-way needle into the lyophilized powder for reconstitution, and the reconstituted vial infused over 5-10 minutes, at 65 IU/kg once weekly for 48 weeks. Emicizumab (Hemlibra®) is an FDA-approved agent for the prevention of bleeding in hemophilia A. It is a subcutaneous agent supplied in vial sizes of approximately 30 mg per ml, 60 mg per 0.4 ml, and 105 mg per 0.7 ml. A tuberculin syringe allows transfer of the drug from the vial for subcutaneous injection over 1-2 minutes, at 1.5 mg/kg weekly (following a 4-week induction with 3.0 mg/kg/week) for up to 48 weeks. **Trial Arms** Arm A Eloctate 100 IU/kg IV qod plus Emicizumab 1.5 mg/kg SQ weekly (after 3.0 mg/kg/wk x 4 wk) for 48 weeks Eloctate 100 IU/kg IV god alone for 48 weeks Arm B

The Inhibitor Eradication Trial (ERADICATE): A Phase III Multicenter, Randomized, Controlled Trial, Comparing *Eloctate* Immune Tolerance Induction (ITI) plus Emicizumab vs. Eloctate ITI Alone

This is a prospective, multicenter, randomized phase III 48-week clinical trial, comparing rFVIIIFc (Eloctate[®]) Immune Tolerance Induction (ITI) plus Emicizumab (Hemlibra[®]) vs. Eloctate ITI alone in severe hemophilia A patients with current or past high-responding inhibitors (anti-FVIII \geq 5.0 B.U.) to eradicate inhibitor formation. Subjects will include male adults or children who are ITI-refractory or ITI-naïve, or who developed an inhibitor on the linked Inhibitor Prevention Trial. We

to Eradicate Inhibitor Formation in Severe Hemophilia A.

PROTOCOL SUMMARY

Study Description:

Title:

Study Duration: This is a 48-week outpatient trial in which all subjects will be randomized to one of two treatment arms and followed for 48 weeks.

Abstract

This is a multi-center randomized phase III clinical trial, the Inhibitor Eradication Trial, in which Eloctate (rFVIIIFc) ITI plus Emicizumab (hemlibra) will be compared with Eloctate ITI alone, using Bayesian platform design to eradicate inhibitors in patients with severe hemophilia A. This design is necessary as randomized trials in rare diseases are often not possible. The INHIBIT Clinical Trials Platform includes two linked trials, the Inhibitor Prevention Trial (Prevention Trial) and the Inhibitor Eradication Trial (Eradication Trial) that will be conducted at up to 41 U.S. hemophilia treatment centers (HTCs) affiliated with universities. The Inhibitor Eradication Trial is a 48-week randomized phase III trial, in which 90 previously treated patients (PTPs) with severe hemophilia A and current or past high-responding inhibitors (anti-FVIII > 5.0 B.U.) will be enrolled. Subjects will include individuals with severe hemophilia A who develop inhibitors during the linked Inhibitor Prevention Trial and adults or children at the same HTCs who are immune tolerance induction (ITI)regractory or ITI-naive. Once enrolled, subjects who meet all the inclusion and none of the exclusion criteria, will be randomized to weekly *Eloctate* ITI plus weekly *Emicizumab* vs. weekly *Eloctate* ITI alone to eradicate inhibitor formation, defined as anti-FVIII<0.6 B.U. Blood draws will be minimized to 6 timepoints, baseline, 4, 12, 24, 36, and 48 weeks postrandomization, and validated for small volumes, 3.8 cc (¾ tsp) each. The Inhibitor Eradication Trial is considered greater than minimal risk as study drug is given before the first bleed and special inhibitor studies are obtained. (NB: The Inhibitor Eradication Trial (PRO19070080) is linked to the Inhibitor Prevention Trial (PRO19040140), as part of the INHIBIT Clinical Trials Platform, and both trials will be conducted efficiently in the same hemophilia treatment centers (HTCs), with the same MDs, coordinators, visit frequency, blood sampling, and assays.

Protocol Title: The Phase III Multicenter, Randomized Controlled Inhibitor Eradication Trial, comparing *Eloctate* Immune Tolerance Induction (ITI) plus *Emicizumab* vs. *Eloctate* ITI alone to Eradicate Inhibitor Formation in Individuals with Severe Hemophilia A.

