3.2 Research Design and Methods

This is a 48-week outpatient, randomized phase III clinical trial that employs Bayesian Platform design to assess inhibitor eradication in patients with severe hemophilia A, FVIII <0.01 IU/ml, and a current or past high-responding inhibitor (anti-FVIII >5.0 B.U.), ITI-refractory or ITI-naive. Because hemophilia is a rare disease, we incorporated Bayesian Platform design and will use historical and prospective ongoing clinical trial data on inhibitor formation (Bayesian "priors") to efficiently use rare patients and increase power. The Inhibitor Eradication Trial is linked to the Inhibitor Prevention Trial, and the trials are integrated so there is efficiency and economy, using the same HTCs, staff, frequency of blood sampling, visits, data collection, and lab assays. The Eradication Trial is a randomized phase III open-label trial designed to evaluate the efficacy of *Eloctate* immune tolerance induction (ITI) (100 IU/kg every other day) plus weekly *Emicizumab* 1.5 mg/kg weekly (after a 4-week induction) vs. Eloctate ITI alone (100 IU/kg every other day), to eradicate inhibitor formation in adults or children with severe hemophilia A and current or past high-responding inhibitors to FVIII, anti-FVIII \geq 5.0 B.U. Approximately 2-4 children or adults with severe hemophilia A and inhibitors will be recruited at each HTC. The study drugs will be administered to each subject for up to 48 weeks. *Eloctate* will be given either by weekly intravenous infusion over 5-10 minutes, and (Eloctate) will be given by weekly subcutaneous injection over 1-2 minutes. For treatment of breakthrough bleeds, for safety reasons, rFVIIa will be given by intravenous infusion over 5-10 minutes at 90 mcg/kg per standard of care, at MD discretion, or if the inhibitor titer has fallen, additional Eloctate will be given, per MD discretion. The treating physician may be the study physician. FEIBA will not be allowed on the trial as it may result in thrombosis or thrombotic microangiopathy in patients taking Emicizumab. All bleeds and study drug(s) will be recorded by patient or parent/ caretaker for each subject in a patient diary. All randomized subjects will be followed 48 weeks or until they reach the study outcome of inhibitor eradication. Follow-up visits will be monthly until end-of-study, week 48.

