This is a randomized Phase III Clinical Trials Platform that includes 2 clinical trials, the **Prevention Trial** (PRO19040140) and the **Eradication Trial** (PRO19070800) in a rare population which utilizes the same HTCs, sampling time, volume, and frequency, visits, and lab assays to enhance trials efficiency. In the **Eradication Trial**, study drug will be initiated as early as the day of enrollment and randomization. Subjects will receive *Eloctate* ITI 100 IU/kg every other day plus weekly *Emicizumab* 1.5 mg/kg (after standard 3.0 mg/kg/wk x4 wk induction) or *Eloctate* ITI 100 IU/kg every other day alone. The doses of these drugs are consistent with standard of care guidelines for bleed eradication (immune tolerance). Subjects will receive the drug(s) to which they are randomized, preferably between 7 am and 9 am on days they are given and continued through study week 48. All bleeds and factor use will be recorded in the Subject Diary. This is an open-label trial, so subjects enrolled on the study will receive study drug by physician prescription. Baseline variables, all potential risk factors, including age, family history of inhibitors, race, and circumcision, will be collected prior to randomization and prior to initiating study drug. (Circumcision is commonly performed in over 50% of children with hemophilia in the U.S., but not an established risk for inhibitor formation).

Bleeding Episodes Occurring during Study

For breakthrough bleeds occurring during the study, *Eloctate* 65 IU/kg will be the treatment of choice for non-inhibitor or tolerized inhibitor patients (BU< 0.6 BU), while rFVIIa 90 mcg/kg will be the treatment of choice for inhibitor patients unresponsive to *Eloctate* or FVIII, per discretion of the treating physician (may be the study physician). The HTC coordinator will review study drug(s) supply with the patient/ parent/ caretaker to assure they are re-ordered when three doses are left. There will be no change in study visits.

Subjects Developing the Primary Endpoint

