- The patient or parent/caretaker will obtain *Eloctate* with/without *Emicizumab* by physician prescription through a clotting factor pharmacy of their choice. *Eloctate* will be administered by venipuncture, using a winged infusion needle (butterfly needle), heplock, or, if required, by central line per physician discretion, over 5-10 minutes. *Emicizumab* will be administered by subcutaneous injection, using a small tuberculin needle over 1-2 minutes. It is anticipated in children and some adults that all study drug doses will be administered in the Hemophilia Center, or, for those living a distance away from the HTC, at a nearby infusion center, emergency room, by patient or parent/ caretaker if trained, or by a visiting nurse.
- All doses of study drug(s), including day, date, time, and dose will be recorded in subject diaries. All bleeds, including day, date, site, and resolution will be recorded by the patient or parent/caretaker. All diaries will be returned to the HTC nurse coordinator at the monthly visits.
- Subjects will begin *Eloctate* with/without *Emicizumab*, with the first dose as early as the day of consent and randomization, should the subject already have received a prescription and supply of study drug as part of standard care; otherwise, study drug(s) may be started as soon as the prescription is received.
- The weekly dose of study drug, 100 IU/kg *Eloctate ITI* with/without 1.5 mg/kg *Emicizumab* (following the 3.0 mg/kg weekly x 4 weeks induction), will be begun following enrollment and screening. The HTC nurse will discuss study visit scheduling with the patient or parent /caretaker. The Screening/ Baseline visit, which may include randomization ant treatment initiation, will last approximately 1 hour.

FOLLOW-UP VISITS:

Study Visit 2: Week 4 (Month 1) Follow-up Visit

- Subject diaries will be reviewed for accuracy and completeness. Data will be extracted for frequency, type, and site of bleeds, including site, and for factor usage by day, date, time, and dose.
- Study drug(s) use will be reviewed and more *Eloctate* with/without *Emicizumab* ordered as needed.
- Concomitant medications will be recorded.
- Assessment for adverse events will be completed.
- Vital signs [blood pressure (BP), pulse (P), respiratory rate (RR), and oral temperature (°C)] will be taken, and weight (kg) will be obtained.

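### The assigned Eloctate regimen is 100 IU/kg every other day, but the Summary says 65 IU/kg once weekly (18.6% of the intended weekly dose) and the Visit 1 text calls 100 IU/kg the weekly dose (28.6% if taken literally)

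*Combined protocol and SAP*

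**What the plan says.** **The assigned regimen.** The Trial Arms entry in the Protocol Summary gives Arm A as "Eloctate 100 IU/kg IV qod plus Emicizumab 1.5 mg/kg SQ weekly" and Arm B as the same Eloctate dose and frequency alone. Section 3.2 agrees, both in its design paragraph ("vs. Eloctate ITI alone (100 IU/kg every other day), to eradicate inhibitor formation") and in the later description of the arms ("ITI 100 IU/kg every other day plus weekly" Emicizumab). Section 3.4 Intervention gives the same dose and frequency. Specific Aim 1, Hypothesis 1 and the Treatment Period text in section 3.2 give the same frequency.

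**Text that states a different dose schedule.**
- Protocol Summary, intervention description: "and the reconstituted vial infused over 5-10 minutes, at 65 IU/kg once weekly for 48 weeks".
- Section 3.2, Study Visit 1: "The weekly dose of study drug, 100 IU/kg", a label that covers Eloctate with or without Emicizumab.

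**Text that states a weekly Eloctate frequency without a dose.**
- Abstract: subjects "will be randomized to weekly *Eloctate* ITI plus weekly" Emicizumab or to weekly Eloctate ITI alone.
- Section 3.2, design paragraph: Eloctate "will be given either by weekly intravenous infusion over 5-10 minutes". The same sentence continues "and (Eloctate) will be given by weekly subcutaneous injection over 1-2 minutes", where the drug name is evidently a slip for Emicizumab.

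**The other use of 65 IU/kg.** In section 3.2 (Treatment Period and Bleeding Episodes) it is the Eloctate dose for a breakthrough bleed once the inhibitor is absent or tolerized.

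**The concern.** The Summary's intervention description and its Trial Arms differ in both dose and frequency, so they cannot both be the regimen. The 65 IU/kg figure cannot be the bleed dose in that sentence, because bleeds are not treated once a week for 48 weeks. The Visit 1 wording matters because treatment starts under that text.

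Eloctate is the backbone of Arm A and the whole of the assigned treatment in Arm B. It is prescribed locally at up to 41 sites expected to enrol 2-4 subjects each, drawn from the subject's own supply, and often given at home. A site that followed either line would give, on average, less than a third of the intended weekly dose. The Equipoise text in section 2.1 rests the hope of faster eradication on small studies of the 100 IU/kg alternate-day regimen, so underdosing would mean testing something else. The documents give no basis for saying how a misreading would split between the arms, and no such claim is made here.

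**Working it through.** The plan states no weekly or cumulative Eloctate total, so there is no figure of its own to reproduce. The check is dose arithmetic.

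**Inputs**
- Intended: 100 IU/kg every other day (Trial Arms; sections 3.2 and 3.4).
- Summary intervention description: 65 IU/kg once weekly.
- Visit 1 text, read literally: 100 IU/kg once weekly.
- Duration: 48 weeks = 336 days.

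**Weekly average.** Alternate-day dosing averages 7/2 = 3.5 infusions per week, so the intended dose is 100 × 3.5 = 350 IU/kg per week.
- Summary: 65/350 = 18.6%; 350 − 65 = 285 IU/kg per week too low; 350/65 = 5.4-fold.
- Visit 1: 100/350 = 28.6%; 350 − 100 = 250 IU/kg per week too low; 350/100 = 3.5-fold.

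**Sensitivity to the averaging.** A single calendar week holds 3 or 4 alternate-day infusions (300 or 400 IU/kg).
- Summary: 65/300 = 21.7% or 65/400 = 16.3%.
- Visit 1: 100/300 = 33.3% or 100/400 = 25.0%.

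**Up to the week 4 visit**, the first scheduled diary review of dosing. This assumes the first dose on day 0 and the week 4 sample drawn before that day's dose. Alternate-day infusions fall on days 0, 2, …, 26, which is 14. Weekly infusions fall on days 0, 7, 14 and 21, which is 4.

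**Over 48 weeks**, if ITI runs throughout: 336/2 = 168 alternate-day infusions, or 48 weekly ones.

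| Schedule | To week 4 | Shortfall at week 4 | To week 48 |
|---|---|---|---|
| Intended | 14 × 100 = 1,400 IU/kg | – | 168 × 100 = 16,800 IU/kg |
| Summary text | 4 × 65 = 260 IU/kg | 1,140 IU/kg | 48 × 65 = 3,120 IU/kg |
| Visit 1, literal | 4 × 100 = 400 IU/kg | 1,000 IU/kg | 48 × 100 = 4,800 IU/kg |

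The Abstract and the weekly sentence in section 3.2 carry no dose, so no percentage is attached to them. The Schedule of Events has no row for dose or frequency and cannot settle the conflict.

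**The case against.** The strongest reply is that no reader could mistake the regimen. The correct one appears in the Trial Arms of the same Summary and again in sections 3.2 and 3.4, and the 65 IU/kg line sits in a product description among vial sizes and infusion times. In the Visit 1 sentence a single adjective covers two drugs and is right for Emicizumab, so it may be only a loose label. There are also safeguards. Section 3.4 has the database track each prescription and infusion, with the schedule stated correctly there, and coordinators review drug supply. The 48-week totals assume that ITI never stops, although section 3.2 foresees stopping it after eradication.

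Much of this stands. Intent is clear, no misdosing is known, tracking could catch an error, the Visit 1 percentage holds only on a literal reading, and the 48-week totals are an upper case. It limits the weight of the point but does not remove it. The 65 IU/kg sentence has no innocent reading, and tracking cannot judge adherence cleanly against a protocol that states two regimens.

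Sections 2.1 and 4.5 also contain looser weekly wording. The remark in section 3.6 about continuing at least weekly concerns treatment after a breakthrough bleed; it neither supports nor undercuts this point.

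**Conclusion.** The concern holds: the text is wrong as written and should be fixed. The Summary states 18.6% of the intended weekly Eloctate dose, and the Visit 1 instruction, taken literally, states 28.6%. Two further places give a weekly frequency without a dose, and one of them also names the wrong drug. The figures assume that 100 IU/kg every other day is the intended regimen, which the documents support throughout, and that alternate-day dosing averages 3.5 infusions per week. This is a drafting error in dosing text. It does not put the design in doubt, and no estimand, sample size or analysis depends on it.

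**What to change.** Once the sponsor has confirmed the regimen, amend four places: the intervention description in the Protocol Summary, the Abstract, the design paragraph of section 3.2, and the Visit 1 instruction in section 3.2. Suggested wording: *Eloctate 100 IU/kg IV every other day in both arms; Arm A only: Emicizumab SQ 3.0 mg/kg weekly for 4 weeks, then 1.5 mg/kg weekly.* In the section 3.2 sentence, change the drug given by subcutaneous injection to Emicizumab. Keep 65 IU/kg only as the bleed-treatment dose. Send sites a short memo stating the correction. Tidying the looser weekly wording at the end of section 2.1's rationale and under Potential Benefits in section 4.5 is optional.

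The cost is a wording amendment and a memo, with no change to design, sample size or analysis.

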1.0 Objective and Specific Aims

The purpose of the Inhibitor Eradication Trial is to eradicate inhibitor formation in children and adults with severe hemophilia A. This 48-week phase III open-label, randomized, controlled trial, comparing *Eloctate* immune tolerance induction (ITI) plus the bispecific monoclonal antibody FVIII mimic, Emicizumab, vs. Eloctate ITI alone, to eradicate inhibitor formation in children and adults with severe hemophilia A, including those developing inhibitors in the Prevention Trial or those ITI-refractory or ITI-naïve never-tolerized inhibitors at the same HTCs. In this trial, time to inhibitor eradication with Eloctate ITI plus Emicizumab vs. Eloctate ITI will be assessed in the eradication of inhibitor formation in children and adults with severe hemophilia A and current or past high-responding inhibitors, defined as anti-FVIII > 5.0 B.U. The research in this trial is considered greater than minimal risk as it involves combining agents to eradicate inhibitors and obtaining special inhibitor studies. The primary endpoint will be the probability of inhibitor eradication by 48 weeks, defined as anti-FVIII < 0.6 B.U. by chromogenic Nijmegen Bethesda assay (CBA), repeated immediately and confirmed within 4 weeks. Secondary endpoints will include a) safety, measured by frequency of bleeds (hematomas, joint, CNS bleeds) and b) mechanism of inhibitor eradication, measured by FVIII-specific T cell ELISPOT assay, performed on peripheral blood mononuclear cells (PBMCs) at baseline and at 4, 12, 24, 36, and 48 weeks. The B cell, Ig, and RNA assays and cytokine assays will be performed on an aliquot of PBMCs to determine the role of T regs in eradication of immune response to FVIII. Studies will be performed on T cell populations depleted of regulatory T cells (T reg) (CD4+CD25+FoxP3+) to determine the role of T regs in controlling immune response to FVIII. Hemophilia genotype and HLA assays will be determined at baseline on the buffy coat of plasma. A microbiome (stool sample) will be obtained at baseline. The trial will assess inhibitor eradication after each subject completes the 48-week trial. The Inhibitor Eradication Trial is designed to test whether Eloctate ITI plus Emicizumab is superior to Eloctate ITI alone in inhibitor eradication by 48 weeks. At the interim, once 75% of the subjects are randomized, the Bayesian posterior probability that either arm, Eloctate ITI plus Emicizumab or Eloctate ITI alone, is more likely to be inhibitor-free must be at least 99.5% to stop the trial. Assuming that the trial does not stop at the interim to declare superiority at the end of the trial, the Bayesian posterior probability that either arm, *Eloctate ITI plus Emicizumab* or *Eloctate ITI* alone, is more likely to be inhibitor-free must be at least 97.9%. This maintains the type 1 error at 5% with at least 80% power for superiority if we assume that the true condition is that Eloctate ITI plus Emicizumab is 15% superior to Eloctate ITI alone (95% vs 80% inhibitor-free).

2.0 Background and Significance

2.1 Background

Hemophilia A is an X-linked inherited bleeding disorder caused by deficient or defective coagulation factor VIII (FVIII) that affects approximately 20,000 in the U.S. and 80,000 worldwide. It is characterized by spontaneous and traumatic bleeding into joints, soft tissue, and muscles. Among the most severe complications of hemophilia treatment is the formation of inhibitor alloantibodies directed against exogenous factor VIII which occurs in up to 30% or more of hemophilia inhibitor patients. Inhibitor formation is a T cell-dependent B-cell immune response, which was first recognized in HIV(+) hemophilia inhibitor patients whose inhibitors disappeared when CD4+ T cells fell below 200/µl and re-appeared after HIV antiviral therapy restoration of CD4 cells to >200/µl. Inhibitor formation typically occurs early in life, after a median of 10-20 exposure days. Inhibitors bind to exogenous FVIII, neutralize its activity, interfering with clinical hemostasis and, despite bypass therapy (e.g. rFVIIa or factor IX concentrates) often leads to uncontrolled bleeding and increased morbidity, cost, hospitalization. Thus, inhibitors are a major cause of morbidity and high healthcare cost. CDC studies have determined inhibitor patients are twice as likely to require hospitalization for bleeding complications and cost on average ten times more than hemophilia patients without inhibitors.

Medical management of individuals with inhibitors is difficult. The use of bypass agents, including the response of inhibitor patients to alternative or bypass agents, such as factor rVIIa or activated IX, which is somewhat unpredictable and suboptimal, and morbidity is high as are healthcare costs. For over 30 years, the only approach to eradication of inhibitors has been immune tolerance induction therapy (ITI), a program of regular FVIII infusions over a prolonged period

of time, which is inconvenient, expensive, and effective in only 75-80% of those treated. Thus, a major goal of comprehensive hemophilia care is to *eradicate* them once they occur, incorporating potentially more effective therapies, such as the novel therapies in development and FDA-approved, e.g. *Eloctate* and *Emicizumab*, to promote better outcomes in those with hemophilia.

Equipoise: We are in a state of equipoise as the optimal approach to eradicate inhibitors in hemophilia is not known. While a randomized trial established that 200 IU/kg daily has been adopted as the standard of care for immune tolerance induction (ITI). However, only 70-80% respond, and ITI is time intensive, burdensome, taking up to 9-12 months with some requiring ports and lines, and costly. Further, those not tolerized within the first year of inhibitor onset are often refractory to ITI. Thus, simpler, more effective approaches to eradicate inhibitors is critical to improve outcomes. With the availability of Eloctate, small studies of ITI using 100 IU/kg every other day has reduced time to inhibitor eradication by nearly 50%, but these studies were not randomized. Among the reasons time to ITI eradication is long is the problem of breakthrough bleeds, which may activate the immune system "danger", and thus, use of Emicizumab by promoting hemostasis and avoiding factor VIII, could potentially reduce bleeds during ITI and reduce time to ITI. However, no data exist on whether Emicizumab reduces time to ITI. However, if breakthrough bleeds occur on Emicizumab, the requirement for FVIII to treat these bleeds could negate the potential effect of Emicizumab on ITI could be lost. In small nonrandomized studies, Emicizuab have indicated it is safe in infants but there are no data and no randomized trials to determine who might benefit or the optimal dose and/or combination of these agents to shorten ITI.

Eloctate (rFVIIIFc) is an FDA-approved FVIII protein that fuses recombinant a FVIII-Fc fusion protein that prolongs FVIII half-life in the circulation and induces regulatory T cells (Tregs) to promotes tolerance to the hapten to which it is attached, i.e FVIII. Eloctate prevents and treats bleeds in hemophilia A patients of all ages. It remains an important question, whether promoting Tregs reduces time to inhibitor eradication (ITI). In patients who develop an inhibitor, the inhibitor neutralizes FVIII activity, and bypass therapy (rFVIIa, FEIBA or factor VIII inhibitor bypass activity) is used to treat bleeds, but at least 50% are unresponsive to bypass agents or have a persistent shortened FVIII half-life. Thus, while it is standard of care to attempt immune tolerance induction (ITI) in patients with inhibitors, the burden of daily infusions and intercurrent bleeds, persistent shortened FVIII half-life even if successful ITI is achieved is significant, and it is not possible to predict the 20-30% who will not respond to ITI. In small, non-randomized studies, *Eloctate* ITI, when given at 100-200 IU/kg/day to hemophilia A patients with existing inhibitors, never tolerized, or previously refractory to ITI, has been shown to shorten the median time to inhibitor eradication, defined as anti-FVIII < 0.6 BU, was 33.8 months in 4 first-time ITI patients and 67.7 months in 4 rescue ITI patients (Carcao). These data suggest there may be potential utility of *Eloctate* in inhibitor eradication.

Emicizumab (Hemlibra) is an FDA-approved bispecific monoclonal antibody that mimics FVIII and has been shown to be safe and effective in phase III trials in hemophilia A with (Oldenburg) or without inhibitors (Mahlangu), as well as in children (Young) and is increasingly being used because of its simpler subcutaneous route. Whether *Emicizumab* may promote inhibitor eradication by avoiding bleeds during ITI and may reducing "danger" is not known. Further, whether *Emicizumab* potentiates *Eloctate* ITI in shortening the time to inhibitor eradication in severe hemophilia A patients with inhibitors is not known.

For these reasons, we will study if *Eloctate* ITI plus *Emicizumab* is superior to *Eloctate* ITI alone in eradicating inhibitor formation in patients with severe hemophilia A and inhibitors to FVIII of all ages, and anti-FVIII > 5.0 B.U. when continued weekly for 48 weeks to eradicate inhibitors. We *hypothesize* that *Eloctate* ITI upregulation of T regs, and *Emicizumab* prevention of bleeds ("danger") will be superior to *Eloctate* ITI alone in eradicating inhibitor formation. The concept is innovative, as it combines the "avoidance of danger" concept with the "promotion of tolerizing T regulatory cells" to improve inhibitor eradication. The concept of avoiding FVIII exposure by preventing bleeds with *Emicizumab* during ITI may be important in eradicating inhibitor formation. It's effectiveness in preventing bleeds in hemophilia inhibitor patients makes it a potentially powerful agent in the management of hemophilia, but there are no data on its use in eradicating inhibitors. Further, if it is not successful in preventing breakthrough bleeds during ITI may negate its potential beneficial effect and simpler subcutaneous administration.

Specific Aim 1: To compare *Eloctate* immune tolerance induction (ITI) every-other-day (q.o.d.) plus *Emicizumab* weekly prophylaxis vs. *Eloctate* ITI q.o.d. alone for 48 weeks in eradicating inhibitors in children and adults with severe hemophilia A in the Eradication Trial. We will conduct this multi-center, randomized phase III clinical trials at up to 41 HTC sites, with the same study visit frequency, blood sampling, and lab assays as in the companion Prevention Trial (PRO 19040140). The primary endpoint in the Eradication Trial is the eradication of anti-FVIII antibody < 0.6 BU by chromogenic Nijmegen-modified Bethesda assay (CBA) by 48 weeks.

Hypothesis 1: We hypothesize that Eloctate ITI q.o.d. plus weekly Emicizumab is superior to Eloctate ITI q.o.d. alone in eradicating inhibitors, anti-FVIII < 0.6 B.U. (CBA), when given for 48 weeks in children and adults with severe hemophilia A and high-responding inhibitors (historic anti-FVIII > 5.0 B.U.). Yet there is equipoise, as while Eloctate ITI may reduce the time to tolerance it is burdensome with qod dosing and data are available from small, nonrandomized studies. While both drugs may shorten ITI and even be synergistic, there is equipoise in the absence of randomized trials. While Emicizumab has been tried in hemophilia A inhibitor patients in small nonrandomized studies, there are no data on whether it reduces time to tolerance. As *Emicizumab* is given subcutaneously weekly, if, when given with *Eloctate ITI*, it was superior to *Eloctate* ITI alone in reducing time to ITI, it would be the "winner" over *Eloctate ITI alone*.

Specific Aim 2: To evaluate the safety and mechanism of inhibitor suppression *eradication* in patients with severe hemophilia A and inhibitors. Secondary endpoints include a) *safety,* measured by number and frequency of bleeding episodes (i.e. hematomas, hemarthroses) and associated factor use and port infections; and b) *mechanism of inhibitor suppression eradication,* measured by FVIII-specific T cell ELISPOT assay; FVIII genotype; HLA type; and chromogenic FVIII trough levels; and by micriobiome stool sample, each compared with anti-FVIII.

Hypothesis 2: We hypothesize that safety, measured by bleeds requiring rescue factor or prophylaxis escalation, and port infections, will not differ between treatment arms; and the mechanism by which *Eloctate* suppresses (prevents, eradicates) inhibitor formation is via Fc induction of regulatory T cells (Tregs) promoting FVIII tolerance, measured by ELISPOT assay. This novel approach to eradicate inhibitors is compelling, and, if successful, will reduce the burden of inhibitor formation and the associated morbidity, hospitalization, cost, and early mortality, and be adopted immediately into clinical practice.

The Inhibitor Eradication trial is a 48-week outpatient trial conducted in 90 inhibitor patients from up to 41+ Hemophilia Treatment Centers (HTCs) (2-4 subjects locally). Case report forms and laboratory assessment forms will be completed and uploaded to a web-based database. While small, nonrandomized studies have suggested that *Eloctate* ITI may shorten inhibitor eradication, and that Emicizumab may eradicate inhibitors in some patients who are ITI refractory or ITI naive, inhibitor formation remains a major complication of hemophilia for which the optimal approach is not known. Further, whether *Eloctate* can potentiate the effect of *Emicizumab* or prevent bleeds during ITI and improves the proportion who are tolerized remains unknown. A single non-randomized trial of Emicizumab in inhibitor patients has been initiated, but data are not available on its impact on inhibitor eradication or time to eradication. Despite these small studies, effective inhibitor eradication remains a compelling problem, for which an effective approach would be practice changing.

2.2 Significance: Inhibitor formation is the most serious complication of hemophilia, affecting 25-30% of those with severe hemophilia A. Inhibitor formation is a T cell-dependent B-cell response to exogenous FVIII that renders lifesaving factor treatment ineffective and leads to poorly controlled bleeding, severe morbidity, frequent hospitalizations, and high healthcare costs. Thus, *eradicating* inhibitors *once* they occur would promote better health outcomes for children and adults with hemophilia, an approach that would be adopted immediately into clinical practice. The drugs we will study are FDA-approved and safe and effective in preventing bleeds in adults and children with hemophilia A, and preliminary data from small studies support the need for clinical trials to determine optimal use of these agents to eradicate inhibitor formation in severe hemophilia A. The Inhibitor Eradication Trial is innovative as it uses a Bayesian Platform design to compare novel agents in a randomized phase III trial. Subjects who enroll in the Eradication Trial will include those with those who develop inhibitors on the companion Prevention Trial (PRO19040140), to compare time tolerance with single or combination novel agents. The two trials are integrated for efficiency and conducted at the same HTCs, with the same visit frequency, blood draws, and lab assays. Moreover, as promising new agents emerge, they could potentially be incorporated into the trial platform design. Finally, the findings of this trial will potentially provide new information on treatment of a major complication of hemophilia and promote blood product safety, per the goals of Healthy People 2020.

